Primary and key secondary analyses of efficacy will be based on the Intent to Treat (ITT) population. Other efficacy analyses will be performed based on the Full Analysis Set (FAS). See section 11.2 for definitions.

The primary efficacy endpoint will be calculated at each time point as a total score based on 11 domain ratings. Changes from Baseline to post-treatment visits will be summarized by treatment group at each study visit. For the CGI-I the observed values will be summarized.

Change from baseline to end of treatment will be analysed using general linear model. Improvement during the run-in period may be included as a covariate. The statistical significance of changes

CONFIDENTIAL

Protocol No: AMO-02-MD-2-003 AMO Pharma Ltd.

from baseline over time may also be assessed using the linear mixed effects repeated measures model.

Due to COVID-19 related restrictions some of the data at certain visits may be collected using a telehealth approach while other data may be collected during in-clinic visits. To evaluate the consistency of telehealth data and in-clinic data for the CDM1-RS and CGI rating scales and to minimize the potential bias, Baseline (, Week) and Week) visits will be performed using both in-clinic and telehealth data collection approaches. Analysis to evaluate the consistency of these two methods of data collection will be performed.

According to the recommendations in the FDA Guidance "Statistical Considerations for Clinical Trials During the COVID-19 Public Health Emergency", sensitivity analyses will be performed in addition to the primary analysis (FDA, 2020). The sensitivity analyses will include combined use of telehealth and in-clinic data; the impact of using telehealth data on outcomes will be evaluated.

The exploratory endpoint analysis will be outlined in the SAP. The details of the analysis methods will be determined after exploratory endpoint data review.

NUMBER OF STUDY CENTERS

Up to 14 sites in the US, UK, Canada, Australia, and New Zealand

ESTIMATED FIRST SUBJECT SCREENED

SUBJECT

Q1 2021

ESTIMATED LAST

O4 2022

LAST VISIT

Protocol No: AMO-02-MD-2-003 AMO Pharma Ltd.

Table 1: Standard Schedule of Events

Visit ²⁵ Screening Run-in Baseline h Interim Interim h Interim h Interim h Interim h Interim h Interim Interim h Interim Interi	[Follow st -up]h,24

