7. SELECTION AND WITHDRAWAL OF SUBJECTS

7.1 Subject Numbers

Approximately 56 children were planned to be randomized into the study, assuming a dropout rate of 10-13%. After a blinded sample size re-estimation (SSRE), the protocol was amended to allow enrollment of between 56 and 66 children randomized into the study, if feasible.

Randomization will occur in a 1:1 manner such that each treatment group will have approximately 28 subjects (assuming a 10-13% drop-out rate) contributing data to the primary efficacy analysis. Randomization will be stratified by age at the time of screening.

Subjects that withdraw due to COVID-19 related reasons e.g. institutional restrictions, travel restrictions, subject in quarantine, or subject shielding, after receiving randomized

Protocol No: AMO-02-MD-2-003 AMO Pharma Ltd.

treatment may be replaced. Subjects that withdraw from the study after receiving randomized treatment for non-COVID-19 related reasons will not be replaced.

Subject eligibility will not be re-assessed after the run-in period; the run-in period is for the purposes of analysis.

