11.5 Statistical Methods for Efficacy

Primary analysis of efficacy will be based on the ITT population. Additional analysis will be performed based on FAS.

The primary efficacy endpoint (CDM1-RS) will be calculated at each time point as a total
score based on 11 domain ratings. Changes in efficacy variables from the start of the
run-in to Baseline for each subject will be summarized and will
be considered as indicative of the effect of two weeks of Changes from
Baseline to post-treatment visits will be summarized by treatment group (weight
adjusted tideglusib 1000 mg versus Placebo) at each study visit. For the CGI-I the observed
values will be summarized.

Change from baseline to end of treatment will be analysed using general linear model with terms for treatment group, baseline and treatment group by baseline interaction (observed values will be analysed for the CGI-I).

The statistical significance of changes from baseline over time may also be assessed using the linear mixed effects repeated measures model with fixed effect terms for treatment group, follow-up visit and treatment group by follow-up visit interaction. Subject will be included as a random effect and baseline as a covariate.

If covariates/interactions in any model are not statistically significant at the 0.05/0.1 two-sided levels, respectively, they will be excluded from the model. The details will be specified in the SAP.

The key secondary efficacy endpoint for analysis is:

• CGI-I at the end of treatment

The secondary efficacy endpoints for analysis are:

- The change from baseline in the Top 3 Caregiver Concerns VAS total score to end of treatment
- The change from baseline in the CC-CDM1-RS total score to end of treatment

- The change from baseline in CGI-S to end of treatment
- The change from baseline in the CDM1-RS independent central rater total score to end of treatment
- The change from baseline in CGI-S independent central rater score to end of treatment
- CGI-I independent central rater score at the end of treatment
- The change from baseline in 10 Meter Walk/Run (preferred speed and fastest speed) to end of treatment

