6.3 General Derivations

This section provides details of general derivations. Derivations specific to the parameter of interest are detailed within the specific SAP section:

Randomized study treatment

Where mentioned in this SAP, "Randomized study treatment" will relate to double-blind study treatment (either tideglusib or placebo). In the case of the SAF, this means the treatment that the subject received rather than the treatment that the subject was randomized to.

The first administration of randomized study medication is defined as the first dose of study medication after the date/time of randomization.

Phase

Phase is defined as a subject's treatment period where:

- Screening Phase: relates to the period ending the day of Visit and dosing commences the next day.
- Run-In Phase: relates to the period starting the day after Visit and ending immediately before the date/time of randomization at Visit
- Double-blind Treatment Phase: relates to the period starting immediately after the date/time of randomization and ending the day of the EOT visit, Visit
- Post-Treatment Phase: relates to the period starting from the day after the EOT visit, Visit

If a visit is split across 2 days, completion of the full study visit is when all assessments on the 2nd day have been completed. Hence the end date of the visit should be used in phase derivations where applicable.

Definition of study day

Throughout this SAP any references to "Visit XX" refer to the pre-specified visits defined in the protocol. Data listings will additionally present study day. Study day will be calculated relative to the first date of administration of randomized study treatment (Study Day 1). There is no Study Day 0. The day before Study Day 1 is Study Day 1.

Definition of baseline and run-in baseline

Baseline is defined as the last non-missing value or mean values, where assessments are made in triplicate such as for ECGs, prior to the subject receiving randomized study treatment. Scheduled and unscheduled assessments will be considered.

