6.13.1.1 Primary Estimand and Supplementary Analysis

The estimand for the primary efficacy endpoint is the difference between group adjusted means in the changes from baseline in CDM1-RS total score at EOT.

If a subject's in-clinic visit is unavailable, the data will be imputed with the corresponding telehealth assessment. The use of telehealth assessments is thought unlikely to be related to outcome, however, it will be assessed for balance between the treatment groups and sensitivity analyses may be conducted in the event of imbalance.

The null hypothesis being tested for the primary endpoint is that there is no difference in mean change in CDM1-RS total score from baseline to EOT between the tideglusib and placebo treatment groups:

$$H_0$$
: Mean Change_{tideglusib} = Mean Change_{placebo}

The alternative hypothesis is that there is a difference in either direction in the mean change in CDM1-RS total score from baseline to EOT between the tideglusib and placebo treatment groups:

$$H_1$$
: Mean Change_{tideglusib} \neq Mean Change_{placebo}

The analysis will include data from Visit (randomisation) to Visit (EOT) inclusive. Data from other visits will be included in the summaries and listings.

Primary Analysis

The primary estimand will be analysed using a mixed model for repeated measures (MMRM).

The treatment difference between tideglusib and placebo at Visit (EOT) will be estimated as the simple contrast in the treatment effect. The standard error (SE), p-value and 2-sided 95% confidence interval (CI), based on the difference in the Least Squares (LS) means between the two treatment groups will be presented. The LS Means, SE and 95% CI will additionally be presented for each treatment by visit.

The MMRM model will be implemented using restricted maximum likelihood (REML). The Kenward-Roger approximation will be used to estimate the denominator degrees of freedom and standard errors

Initially an unstructured covariance matrix will be investigated. If this analysis fails to converge, the following alternative structures will be tested in the following order until convergence is achieved: Toeplitz, AR(1) and compound symmetry. If a covariance matrix other than unstructured is selected, the estimated standard errors and variance-covariance matrix of the fixed-effects parameters will be computed using a robust "sandwich" estimator (i.e., by specifying the EMPIRICAL option on the PROC MIXED statement).

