The model will contain treatment, age group, visit and treatment by visit interaction as fixed effects, baseline CDM1-RS as a covariate.

If the baseline CDM1-RS and/or age group is not significant at the 15% level (i.e., p>=0.15) then a secondary analysis will be conducted with the term(s) removed from the model. Similarly if the p-value for the treatment by visit interaction is not significant at the 15% level, that term will be removed in the secondary analysis and the LS

Date:22FEB2023 Version: Final 2.0 ST/form/010/15 Means and treatment differences under the assumption of a constant treatment effect over time will be estimated.

Normality of the data will be investigated through plots of the residuals. Non-parametric analyses may additionally be performed if the data are found to be sufficiently non-normal. This will include non-parametric analysis of covariance (ANCOVA) (Koch G.G. et al, 1998 and Zink, R. and Koch, G.G., 2012) of the change from baseline to Visit with treatment, baseline CDM1-RS and age group as covariates.

Any data collected after study discontinuation will not contribute to the treatment effect estimate. Only data up to study discontinuation will be used.

Missing Data

Missing data due to early study discontinuations or missed visits are assumed to be missing at random (MAR) and observed data only will be used for the primary analysis. The MMRM accounts for these missing data using a direct likelihood approach.

Sensitivity Analysis

Several sensitivity analyses will be applied to this endpoint:

Sensitivity analysis 1 – Multiple Imputation: Missing at Random (MAR)

At a visit, if a subject has no in-clinic or telehealth assessment data the visit is assumed to be MAR. This assumes that subjects with missing data follow the same trajectory as other subjects in their respective treatment arm that have complete data.

- Intermittent missing data will first be imputed using the MCMC method, appropriate for non-monotonic missing data.
- Data missing after subjects discontinue the study early will be imputed using a regression, appropriate for monotone missingness. At each time point, missing data will be assumed to follow a distribution similar to scores for subjects who are still in the study and randomized to the same treatment group.

The MI method (as described in Section 6.3) will be employed with the following assumptions/steps:

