- Improvement during the run-in period (Yes, No). Improvement in this case is defined as a 2-point or greater improvement in the total score.
- To identify items which are primarily driving an improvement in CDM1-RS total score, the 11 individual items will each be analysed in an analogous method to the primary estimand above. A forest plot with all 11-items on the y-axis, showing the treatment effect will additionally be provided.
- The occurrence and potential imbalance of intercurrent events (e.g. concomitant medication changes, protocol non-compliance), deaths and COVID-19 impacts between treatment groups will be reviewed after unblinding the randomization.
 - If an imbalance is detected in the intercurrent events, further summaries and/or analyses may be undertaken to assess the impact of this.
 - Deaths are not anticipated during the study. If an imbalance in deaths is determined, a joint rank analysis (based on the change in CDM1-RS from baseline and time to death) may be utilized.

Summaries and Figures

Summary statistics of observed values and change from baseline will be presented by visit and treatment for the in-clinic and telehealth visits separately. For subjects who have both an in-clinic and telehealth assessment at a visit, change from baseline in CDM1-RS will be calculated for both methods and summarised separately.

The observed CDM1-RS total score will be presented over time using by subject line plots by treatment group for the in-clinic and telehealth visits separately. The plots will be presented together but on two separate panels.

Additionally, histograms of the change from baseline at each visit will be presented by treatment group. Empirical cumulative distribution functions (CDFs) of the change from baseline will be presented by treatment group at Visit

The adjusted LS mean changes from baseline and SEs over time will be presented via line plots as estimated by the primary estimand MMRM model by treatment group.

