and treatment by visit by subgroup interaction will be added to the model. Any interactions that are statistically significant at the 15% level for the end of treatment visit will have their nature described. These models will be used to estimate treatment comparisons within the subgroups that correspond with the sub-grouping factor. The results from the analysis are to be presented as described above in tables and/or figures. Subgroups of interest include but are not limited to:

- o Race (White, Non-White)
- Sex (Male, Female)
- o Age group (
- o Improvement in clinician-completed in-clinic CDM1-RS during the run-in period (Yes, No).

Summaries and Figures

Summary statistics of observed values will be presented as both continuous and categorical by visit and treatment for the in-clinic and telehealth visits separately.

By subject line plots of the observed CGI-I results will be presented over time by treatment group. In addition, line plots will present the adjusted LS means and associated SEs for the observed values over time, as estimated by the MMRM model, by treatment group.

For the 3 occasions in the study (Visit and and where dual telehealth and in-clinic assessments are conducted, summary statistics of the difference between the methods (in-clinic – telehealth) will be calculated and summarized using descriptive statistics over time. The intra-rater correlation will also be presented for each visit. A scatterplot for each visit will compare the observed value for the two methods for each subject, with in-clinic assessments being presented on the y-axis and telehealth on the x-axis. A linear regression line separately for each treatment will be included.

A line plot will present the observed values by visit, with in-clinic and telehealth assessments being presented on the same plot. Bar charts of the CGI-I frequency over time will be produced for the in-clinic and telehealth interviews separately. The CGI-I observed value (1 to 7) for Visits and will be presented on the x-axis and the number of subjects will be presented on the y-axis. The proportion of subjects achieving a CGI-I of 1, 2 or 3 will be presented similarly.

Data for in-clinic and telehealth assessments will be listed separately, with whether a telehealth assessment is within the pre-defined visit window for imputation as an inclinic assessment being annotated.

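### The primary CDM1-RS model leaves out the run-in-start score, a pre-randomisation covariate that is already collected and cheap to add; the gain may range from nil to moderate

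*SAP*

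**What the plan says.** Protocol 7.1 states that eligibility is not looked at again after the run-in and that "the run-in period is for the purposes of analysis". The synopsis, under statistical methods for efficacy, adds: "Improvement during the run-in period may be included as a covariate". Protocol 11.5 names no such model term but plans a descriptive use: change from "run-in to Baseline for each subject will be summarized".

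The SAP's primary analysis (6.13.1.1) is a mixed model for repeated measures: "The model will contain treatment, age group, visit and treatment by visit interaction as fixed effects, baseline CDM1-RS as a covariate". Its data window excludes earlier ratings: "The analysis will include data from Visit (randomisation) to Visit (EOT) inclusive". SAP 6.3 fixes the covariate as the value nearest to randomised treatment: "Baseline is defined as the last non-missing value or mean values" before that treatment, so it falls after the run-in. The same section defines a separate run-in baseline (the last value before any study treatment) but assigns it to selected safety data.

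Run-in response reappears among the supplementary subgroup factors in 6.13.1.1 as Yes/No: "Improvement in this case is defined as a 2-point or greater improvement in the total score". For the key secondary endpoint (6.13.2.1) the matching factor is "Improvement in clinician-completed in-clinic CDM1-RS during the run-in" period, again Yes/No. Under both endpoints, a subgroup characteristic judged unbalanced between arms is to be added to the model as a covariate. SAP 6.18, which lists changes from the protocol, does not mention the run-in covariate.

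**The concern.** The run-in does not select children on their response to it; its stated role is analytical. A run-in-start CDM1-RS total must exist for most children, because the plan computes a run-in change from it. A score taken before randomisation cannot be affected by the randomised treatment, so it is a safe covariate. Two ratings may also locate a child's underlying level better than one.

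The setting is one where precision is scarce. SAP section 3 reports 53 children randomised, against about 56 planned and 66 recommended after the blinded re-estimation. The scale is new and rater-scored. Cutting the run-in change at 2 points and using it for subgroups discards information that a continuous term would keep. At stake is some precision in the primary contrast, not its validity.

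**Working it through.** **1. The plan's own power figure.** Protocol 11.1 gives an SD of change of 2.64, a difference of 2.2, 25 per group and 82% power; the level is two-sided 0.05. The noncentrality is 2.2 / (2.64 × √(2/25)) = 2.2 / 0.747 = 2.95 on 48 df. Power is 82.3% by noncentral t (83.8% by normal approximation), so the figure reproduces. It refers to an unadjusted comparison of change scores.

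**2. Sample size for the check.** With 53 randomised and 10-13% dropout, 53 × 0.87 = 46.1 to 53 × 0.90 = 47.7 children remain, about 23 to 24 per group. I use 23.

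**3. Baseline adjustment credited first.** Let b be the baseline–EOT correlation, p the run-in-start–EOT correlation and q the correlation between the two pre-randomisation scores. With equal variances at baseline and EOT, the score variance implied by the change SD is σ² = 2.64² / (2(1 − b)).

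- Baseline only: residual variance = σ²(1 − b²).
- Both scores: residual variance = σ²(1 − R²), with R² = (b² + p² − 2bpq) / (1 − q²).
- If b = p = q = ρ, the ratio of the two is (1 + 2ρ) / (1 + ρ)².

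Worked case, b = 0.75, p = 0.72, q = 0.80: R² = (0.5625 + 0.5184 − 0.8640) / 0.36 = 0.6025. The residual fraction falls from 0.4375 to 0.3975, a cut of 9.1%. With σ² = 6.97 / 0.50 = 13.94, the residual SD falls from 2.47 to 2.35.

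**4. Results at 23 per group, difference 2.2.** The correlations are assumptions. Power is by noncentral t with 42 residual df, then 41 with the extra term (one df is allowed for age group).

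| b, p, q | Cut in residual variance | Power, baseline only | Power, both scores | Gain (points) |
|---|---|---|---|---|
| 0.70, 0.70, 0.70 | 17% | 85.0% | 90.7% | 6 |
| 0.80, 0.80, 0.80 | 20% | 82.9% | 90.1% | 7 |
| 0.90, 0.90, 0.90 | 22% | 80.9% | 89.5% | 9 |
| 0.75, 0.72, 0.80 | 9% | 83.9% | 87.2% | 3 |
| 0.80, 0.76, 0.85 | 6% | 82.9% | 85.2% | 2 |
| 0.75, 0.70, 0.85 | 3% | 83.9% | 85.0% | 1 |
| 0.70, 0.60, 0.85 | 0% | 85.0% | 84.9% | 0 |

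**5. Simulation check** (6,000 trials per case, 25 per group, b = 0.7). With equal correlations, power goes from 86.9% to 91.4% and the mean standard error from 0.691 to 0.638. With q = 0.8 and p = 0.7, power goes from 87.5% to 90.3%. With q = 0.8 and p = 0.56, where the run-in score carries nothing beyond baseline, power goes from 87.1% to 86.2% and the mean standard error from 0.693 to 0.700.

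**6. Same term as the protocol's option.** Once baseline is in the model, adding the run-in-start score or adding continuous run-in change gives the same fit: β₁·base + β₂·start = (β₁ + β₂)·base − β₂·(base − start).

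The calculation is a single-visit ANCOVA. It ignores the intermediate visits and any variance explained by age group.

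**The case against.** The strongest reply is that the return is unknown and may be nil. It depends on how well the run-in-start score predicts EOT once baseline is known, and no document gives that. Protocol 11.5 speaks of two weeks for the run-in effect, and Protocol 10.1.1.1 asks for the same rater throughout. Two ratings close together by one rater should agree with each other more than either agrees with EOT. The fading rows are therefore more plausible than the equal-correlation rows. This stands, and it limits the expected size.

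A reader might also infer that the run-in fails its stated purpose. The documents do not support that. Baseline is taken after the run-in, which keeps early response largely out of the primary change score. Run-in change is summarised, it defines subgroups for the two leading endpoints, and it can enter a model if unbalanced. For the CGI-I, the first rating appears to cover the run-in (SAP 6.13.2; visit numbers are blacked out), and a baseline CGI-I is a covariate in that model.

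Nor is there a breach. The synopsis says the covariate may be included, and Protocol 11.5 does not list it. Adjusting for the stratification factor and one baseline is a complete, standard model.

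What remains is that a continuous covariate, already collected and foreseen by the protocol, is not in the primary model, and the SAP does not say why.

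**Conclusion.** The point holds as an optional, low-cost efficiency improvement. The omission causes no bias and does not affect type I error, and the 82% figure is correct on its own terms.

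Under assumed correlations the cut in residual variance runs from 0 to 22%. At 23 per group this is worth about 0-3 power points if correlation fades with time, from a baseline-adjusted 83-85%. It is worth 6-9 points only if all three correlations are equal, from 81-85%. I regard the lower range as the likelier.

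Two stronger readings should be avoided. One is that precision is certainly lost: the zero-gain row is a realistic possibility. The other is that power would climb from 79% to 83% or 87%, which comes from shrinking the SD of 2.64 by 5% or 10%. That SD belongs to unadjusted change, and the primary model already adjusts for baseline, so its starting power is higher and the plausible gain smaller.

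**What to change.** Before unblinding, pre-specify the continuous run-in-start CDM1-RS total (equivalently, continuous run-in change) as a second covariate in the primary model. Extend the run-in baseline definition in SAP 6.3, now limited to selected safety data, to this score, and state a simple rule for missing values. Keep the 2-point subgroup as descriptive.

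The 2024 addendum describes its own analyses as post hoc, so that moment may have passed. If so, leave the primary model alone and report the two-covariate model as a labelled supportive analysis. In either case, one line in SAP 6.18 should record how the synopsis option was handled.

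Extend this to other scales only where a run-in-start rating is confirmed. It should not be assumed for the Top 3 Caregiver Concerns VAS: Protocol 10.1.2.2 has those concerns chosen and rated at baseline, and the visit numbers are blacked out.

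The cost is SAP wording, one model term and one degree of freedom. If the score adds nothing beyond baseline there is no gain; in the simulated no-gain case the loss was about one power point at 25 per group.
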